9 MEASURES TO REDUCE DEVIATIONS TO MINIMUM

On the other hand, adherence to treatment will be evaluated as follows:

- With the study medication accounting returned.
- Patients will have a "diary of the subject" where time of application of the drop and any incident or mishap at the time of the application of the drop, for example forgetfulness in the application of the drop, application of extra drops etc. will be noted.
- The adherence to treatment must be greater than 80%.

Example:

Favor de anotar con pluma negra y letra de molde los siguientes:			
Fecha:	dd/mm/aaaa	Hora:	hh:mm
A) SI NO COMENTARIOS			
1.-Aplico la gota oftalmica:			sí, NO pase a sección B
2.-Cuantas gotas aplico:	1 	2 	
- Sí fue 2 ó mas explicar: _____			
<hr/>			
B) SI NO COMENTARIOS			
3.-Olvido la aplicación:			
4.-Intento aplicar la gota nuevamente:			
- En caso de sí, anotar la hora: _____			
5.-Cuantas gotas aplico:	1 	2 	_____
- Sí fue mas de 2 explicar: _____			

A meeting of researchers will be organized for the physicians involved in the study before beginning with the inclusion of subjects. And your attendance will be mandatory.

At the end of the study the patients will answer a questionnaire of satisfaction of the subject in the local language and the researcher will explain to the subject how to answer it. It is not authorized for the researcher to report / correct the qualification of the subject in the self-qualification questionnaires.

10 ADMINISTERED PRODUCTS

Table 3. Description of study drugs

Ophthalmic drops PRO157

- Chemical name:

Pazufloxacin mesylate [S - (-) - 10- (1-aminociclopropyl) -9-fluoro-3-methyl-7-oxo-2,3-dihydro-7H-pyrido (1, 2,3-de) (1, 4) -benzoxazine-6-carboxylic acid monomethanosulfate.

[figure not shown]
- Molecular weight:

414.41g / mol

-Molecular formula:

C16H15FN2O4 • CH3SO3H

- Chemical structure:

11 DESCRIPTION OF THE PACKAGING

Multi-dose bottle

Primary packaging

PRO157	PRECAUCIÓN: MEDICAMENTO DE ESTUDIO. LIMITADO SÓLO PARA USO DE INVESTIGACIÓN	Paciente No: _____ Iniciales: _____ No. M.E.: _____ Lote: _____ Cad: _____
Solución oftálmica Contenido: 5 mL		

Secondary package

The primary packaging will be contained in a secondary packaging in which the patient's initials and the researcher's name will have to be noted; It will also contain information on drug management as shown in the example.

Example

No. de medicamento: Lote: Fecha de caducidad:	PRO157 Protocolo: SOPH157 - 0114/II No. de paciente: _____ Iniciales del paciente: _____ Investigador: _____ Vía Oftálmica. Administrar según lo indicado en el protocolo.	DESPRENDER ETIQUETA PRO-157 Protocolo: SOPH157 - 0114/II
---	--	---

12 MANAGEMENT OF THE STUDY MEDICINE

The medications will be supplied from the manufacturing site (Sophia SA Laboratories of C.V.) previously weighed.

The management of the study medication will be under the responsibility of the researcher and / or pharmacist of the health care establishment (when applicable), including:

- The reception and storage of the study medication (ME). The receipt of the study medication will be charged by signing and returning the medication delivery form. The study medication must be stored in a secure area with restricted access. Some special storage conditions are requested
 - The PRO-157 ophthalmic solution should be stored at room temperature to no more than 30 ° C,
 - The bottle must be kept tightly closed.

The investigating doctor or the person previously designated in the delegation of responsibility format is obliged to keep a documented record of humidity and minimum and maximum daily temperatures on one occasion a day, for the realization of these measurements, Sophia Laboratories will provide a thermo hygrometer which will be returned at the end of the clinical study.

- The discharge of the thermo hygrometer data will be done by the clinical monitor during the monitoring visits.
- The expiration date will appear on each box and label of the investigational medication.
- The delivery of the study medication will be in accordance with the study plan and following the delivery methods described in the section. The researcher and / or pharmacist of the health care establishment should use the treatment delivered only for the patients participating in the study.
- The study medication count.

The investigating physician and / or a previously designated responsible person of your study team must fill out in real time all the documents that the sponsor provides for the management of the study medication (acknowledgment of receipt in the shipping formats, tracking form of study medication).

The study monitor will periodically check the management and counting of the medication under study.

At the end of the study, the researcher and the study monitor will perform the final count of the medication, and it will be recorded in the corresponding format.

The study monitor will collect and send to Laboratorios Sophia S.A. of C.V. the remaining study drugs, for storage and subsequent destruction, after quantification thereof.

All defects or deterioration of medications or their packaging must be reported to the study monitor. The investigator will notify the monitor of all complaints received from a patient.

In case of early return of the treatments to the sponsor (withdrawal of the lot), the sponsor will prepare an informative letter addressed to the researcher and / or pharmacist of the health care establishment. This letter will be sent by the people locally responsible for the study. Upon receipt of the letter, the investigator and / or pharmacist will identify the patients who have the treatment in their possession at the time the incident is known, using the tracking form of the study medication, and will contact them immediately. . The monitor will organize the return of the study medication to proceed with its destruction.

13 CENTER CLOSURE

13.1 Premature discontinuation of the study

The sponsor may terminate the study before the scheduled deadline. A written confirmation will be sent to the researcher informing him that the clinical study is terminated.

The investigator will date and sign two copies of the written confirmation (one copy to return to the sponsor and the other copy to file in the Investigator's Study File).

The Ethics Committees and the Competent Authorities will be informed in accordance with local regulations.

13.2 Closure of the center

Any center that has finished including the last patient previously stipulated; and that this has complied with the days of study treatment and the safety visit; It may be closed if there is a common agreement between the sponsor and the study center.

14 DATA SOURCE

The following data (s) will be considered as source:

- The patient's medical file, notes of interconsultation, results of clinical laboratories, results of cabinet examinations.
- Patient's diary,
- Self-qualification questionnaires (subject satisfaction questionnaire)

The patient will directly record the data in the patient questionnaire and in the paper self-assessment questionnaires (subject satisfaction questionnaire), which will be considered source data.

15 SELECTION AND WITHDRAWAL OF SUBJECTS OF STUDY.

Eligibility Criteria

15.1 Inclusion Criteria

All selected subjects:

- They will have an age between 0 to 99 years * see note.
- They will be obtained in the external consultation.
- With diagnosis of bacterial conjunctivitis (signs and / or symptoms and / or culture)
- Signed and dated Informed Consent (Informed Consent and parental consent in case of being a minor)

* NOTE: In the case of inclusion of subjects from 0 years to less 18 years minus 1 day, they will be included progressively as follows:

- Age group of 12 to 18 years.
- Age group from 2 to 12 years old.
- Age group from 0 to 2 years.

This with the intention of integrating patients once the dosage parameters have been established as safe and recommended for the younger age groups.

The indications of the inclusion periods will be made as the results are gathered in the groups of minors.

The Informed Assent will only apply to minors who demonstrate understanding of the study, at the discretion of the researcher.

- Physical examination of patients

In the examination carried out during the baseline visit, a general and ophthalmological clinical history will be performed, initially including and starting treatment with all those patients clinically suspected of bacterial conjunctivitis. If the culture is negative but clinically there is improvement, you can continue with the treatment until the last day of the stipulated study. At the baseline visit a urine pregnancy test will be performed (if applicable).

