4 INFORMATION ABOUT BACKGROUND

4.1 INTRODUCTION

Conjunctivitis (partial or total inflammation of the conjunctiva) caused by an external pathogen can be divided into bacterial and viral, however we must not forget that if we take into account its etiology we can name by fungal, allergic, autoimmune and by physical means (heat burns, friction, chemical).

In the following document, we will concentrate on exposing the epidemiological and clinical panorama of conjunctivitis caused by pathogens (bacteria and viruses) and the suffering related to the mass.

Currently about 6 million cases are registered per year in the general consultation (1% of the total annual consultations), this does not mean that all cases will be sent to the ophthalmologist, however as a reason for consultation 70% of the subjects come first with a family doctor and 35% refer to ophthalmologists because it is a case that does not remit with symptomatic or because the severity warrants it.

The cost of treating conjunctivitis according to data collected in the American union represents more than 377 million dollars a year.

Viral conjunctivitis:

Viral conjunctivitis represents an average of 80% of reported cases, it is estimated that 50% of these will be misdiagnosed as bacterial, this when compared to positive cultures.

65-90% of cases are caused by adenoviruses found in any of its two pathogenic entities, either in the form of epidemic keratoconjunctivitis or pharyngo-conjunctival fever. Clinically both are characterized by local inflammatory reactions, hyaline secretion, chemosis, photophobia, hyperemia, corneal deposits and lymphadenopathy.

The adenovirus is highly contagious and an estimated 10 to 50% chance of spread. 46% of the cultures in the hands of patients diagnosed with keratoconjunctivitis are positive, so their spread is verified mainly by contact and fomites.

Its incubation period ranges from 5 to 12 days and its transmission period of 10-14 days.

Its treatment consists of treating the symptoms with eye lubricants, NSAIDs, eye antihistamines, cold compresses, etc. Prophylaxis with antibiotics is not indicated since its benefit has not been proven, more if complications and delay in diagnosis of other entities are reported.

Bacterial conjunctivitis:

Its incidence is estimated at 135 per 10,000 inhabitants. The main routes of infection are by contact, although the proliferation of normal flora can occur as sole etiology or concomitantly.

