7 STUDY DESIGN

7.1 Point or limit points

Criteria for the evaluation.

Efficacy measurements:

Main efficacy criterion

Efficacy will be determined by taking cultures of the lower conjunctival cul-de-sac background quantifying (colony-forming units) and identifying genus and basal and final microbial species.

It will be determined as effective if there is a reduction in the number or species of bacterial flora comparing the basal culture against the end between the five different groups of patients and / or if there is a reduction or absence of the following specific signs and symptoms: burning, tearing, Foreign body sensation, pruritus, photophobia, conjunctival hyperemia, chemosis, palpebral edema and secretion, membranes and / or pseudomembranes when comparing the study medication versus Moxifloxacin and versus Gatifloxacin from baseline to final visit.

Efficiency parameters

- The effectiveness of the drug will be evaluated by means of:

1. Clinical referral

2. Microbiological remission

Clinical remission will be evaluated by means of the signs and symptoms that the patient presents at the beginning and at the end of the study.

Variable	Operationalization	Measurement scale	Value
Secretion	Dependent Qualitative ordinal	Absent Present	Must be recorded as absent in 95% of the subjects evaluated
Conjunctival hyperemia	Dependent Qualitative ordinal	Absent Mild Moderate Severe	You must comply with the following: • Absent \geq 95.0% • Mild \leq 5.0% • Moderate \leq 2.5% Severe \leq 1.0%
Chemosis	Dependent Qualitative ordinal	Absent Present	Must be recorded as absent in 95% of the subjects evaluated
Eyelid edema	Dependent Qualitative ordinal	Absent Present	Must be recorded as absent in 95% of the subjects evaluated
Corneal epithelial defects	Dependent Qualitative ordinal	Affected area, percentage	Percentage of affected area less than 95%

The microbiological remission will be evaluated by means of the culture taken from the conjunctival sac fundus.

Variable	Operationalization	Measurement scale	Value
Culture	Dependent Discrete quantitative	UFC * / ml Eradication Reduction Proliferation	Must be recorded as absent in 95% of the subjects evaluated

* Colony forming units

The drugs under study will be considered effective if the patient has any of the following:

1. Clinical remission + Microbiological remission.
2. Clinical referral.
3. Microbiological remission.

Security measurements:

Adverse events and visual capacity.

Evaluation parameters

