18.2 Times of Measurements

Clinical examination

Basal visit (Day 1)

The principal investigator or the head of the research team of the site duly specified must obtain the letter of informed consent of each of the subjects, before carrying out any procedure of the study.

When the informed consent is obtained and all the inclusion criteria and none of exclusion are met, a unique identification number of the subject will be assigned, this will be used throughout the study for its identification.

Female subjects who are of reproductive age will be tested for pregnancy in urine.

The following evaluations will be made:

Signature of informed consent

Review of inclusion criteria and exclusion criteria,

Demographics,

Urine pregnancy test (if applicable),

General and ophthalmological clinical history,

Clinical Photography,

Sampling of conjunctival sac fundus for culture,

Assigning number to the subject,

Delivery of medication,

Ocular symptoms: burning, tearing, foreign body sensation, pruritus, photophobia

Visual acuity and / or visual ability,

Anterior biomicroscopy: Conjunctival hyperemia, chemosis, secretion, palpebral edema, membranes and / or pseudomembranes, scales, epitheliopathy,

Fluorescein staining,

Green stain of lysine,
Posterior segment revision: Retina, Macula, Vitreous and Optic nerve.
Evaluation of adverse events.

This day the patient will be included, if clinically it suggests a bacterial conjunctivitis, it will be randomized and at that same moment a clinical photograph of his eyes will be made and a sample will be taken for culture of both eyes, immediately he will go with the person previously designated to randomize him, this person will not be masked and will give specific instructions to the patient on how to apply the study medication and will remember the importance of the patient not mentioning the study's evaluating physician how many times the treatment is applied, then he will start with the study medication regardless of the crop results.

Treatment visits:**Visit 1 (Day 3)**

Between the days of study there may be a window of \pm 1 day. If for any reason an assessment is made on any day not planned in the study, this information should be recorded in the unscheduled visit format found within the FRC.

At each follow-up visit, an ophthalmological examination will be performed in order to evaluate the following parameters.

1. Acuity and / or Visual Ability
2. Clinical Photography,

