ANNEX 1. Calculation of sample size.

Fórmula de Fleiss para el cálculo del tamaño de muestra para proporciones.
 "Statistical Methods for Rates and Proportions" 2a. Ed. Pp. 38-45 Wiley. 1981. EUA.
Casos y Controles.

r = Razón de: Controles : Casos = 1 : 1 1.00

P1 = Eficacia absoluta en el grupo tratado con algun medicamento. 0.6980

Q1 = 1 - P1 0.3020

P2 = Eficacia absoluta en el grupo tratado con placebo. 0.5330

Q2 = 1 - P2 0.4670

P = Proporción promedio ponderada de eficacia absoluta.

$$P = \frac{(P1 + r * P2)}{r + 1} 0.6155$$

Q = 1 - P 0.3845

α = Nivel de significancia o probabilidad de error tipo 1 0.050

$1-\alpha/2$ = Percentil bilateral para el nivel de significancia asignado 0.975

$Z_{1-\alpha/2}$ = $Z_{0.975}$ de la distribución normal estandarizada que deja un area de 0.975 a la izquierda. Implica una confiabilidad del 95% 1.960

β = Probabilidad de error tipo 2 0.200

$1-\beta$ = Percentil unilateral para la beta asignada 0.800

$Z_{1-\beta}$ = $Z_{0.80}$ de la distribución normal estandarizada que deja un area de 0.80 a la izquierda. Implica un poder del 80% 0.842

m' = Tamaño de muestra

$$m' = \frac{(z_{1-\alpha/2} \sqrt{(r+1) * P * Q} + z_{1-\beta} \sqrt{r * P1 * Q1 + P2 * Q2})^2}{r * (P2 - P1)^2}$$

$$m' = \frac{(1.960 \sqrt{(1.00+1) 0.62 * 0.38} + 0.842 \sqrt{1.00 * 0.70 * 0.30 + 0.53 * 0.47})^2}{1.00 (0.53 - 0.70)^2}$$

$$m' = 135.272$$

m = Tamaño de muestra corregido

$$m = 0.25 m' * \left\{ 1 + \sqrt{1 + \frac{2(r+1)}{m' * r * |P2 - P1|}} \right\}^2$$

$$m = 147 \quad \begin{array}{l} \text{Tamaño de muestra para el grupo de referencia (Controles): } m_1 = r * m \\ \text{Tamaño de muestra para el grupo de estudio (Casos): } m_2 = m \end{array} \quad \begin{array}{l} 147 \\ 147 \end{array}$$

Fórmula de Fleiss para el cálculo del tamaño de muestra para proporciones.
 "Statistical Methods for Rates and Proportions" 2a. Ed. Pp. 38-45 Wiley. 1981. EUA.
 Casos y Controles.

r = Razón de: Controles : Casos = 1 : 1 1.00

P1 = Eficacia específica en el grupo tratado con algun medicamento. 0.9234
Q1 = 1 - P1 0.0766

P2 = Eficacia específica en el grupo tratado con placebo. 0.6612
Q2 = 1 - P2 0.3388

P = Proporción promedio ponderada de eficacia específica

$$P = \frac{(P1 + r * P2)}{r + 1} 0.7923$$

Q = 1 - P 0.2077

α = Nivel de significancia o probabilidad de error tipo 1 0.050

$1-\alpha/2$ = Percentil bilateral para el nivel de significancia asignado 0.975

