$Z_{1-\alpha/2} = Z_{0.975}$ de la distribución normal estandarizada que deja un area de 0.975 a la izquierda. Implica una confiabilidad del 95% 1.960

β = Probabilidad de error tipo 2 0.200

$1-\beta$ = Percentil unilateral para la beta asignada 0.800

$Z_{1-\beta} = Z_{0.80}$ de la distribución normal estandarizada que deja un area de 0.80 a la izquierda. Implica un poder del 80% 0.842

m' = Tamaño de muestra

$$m' = \frac{(z_{1-\alpha/2} \sqrt{(r + 1) * P * Q} + z_{1-\beta} \sqrt{r * P1 * Q1 + P2 * Q2})^2}{r * (P2 - P1)^2}$$

$$m' = \frac{(1.960 \sqrt{(1.00+1) 0.79 * 0.21} + 0.842 \sqrt{1.00 * 0.92 * 0.08 + 0.66 * 0.34})^2}{1.00 (0.66 - 0.92)^2}$$

$$m' = 36.373$$

m = Tamaño de muestra corregido

$$m = 0.25 m' * \left[1 + \sqrt{1 + \frac{2(r + 1)}{m' * r * |P2 - P1|}} \right]^2$$

$$m = 44 \quad \begin{array}{l} \text{Tamaño de muestra para el grupo de referencia (Controles): } m_1 = r * m \\ \text{Tamaño de muestra para el grupo de estudio (Casos): } m_2 = m \end{array} \quad \begin{array}{l} 44 \\ 44 \end{array}$$

Analyzed data set

The data will be analyzed in two groups, one will be made up of the population evaluable by Intention to Treat (ITT) in which each of the variables is described, the ITT population will be constituted by all the recruited subjects who have received at least one dose of study treatment.

Others will be the evaluable population Per Protocol (PP) which is the subset of ITT composed of all subjects without any major deviation from the protocol, in which the bivariate analysis will be performed.

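### Neither analysis set requires a positive baseline culture, so eyes without bacteria enter the between-group comparison and shrink differences in the direction of non-inferiority

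*Combined protocol and SAP*

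**What the plan says.** **Entry and dosing.** Under section 15.1 the diagnosis may rest on signs, symptoms or culture, any one of which is enough. In section 18.2 the culture sample is taken at the baseline visit, and "then he will start with the study medication regardless of the crop results". If that culture turns out negative, section 15.1 states: "If the culture is negative but clinically there is improvement, you can continue with the treatment".

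**Analysis sets.** Section 23 defines two. ITT is "all the recruited subjects who have received at least one dose of study treatment" and is used for description; section 15.3 also links it to safety. PP is the part of ITT without a major protocol deviation, and the bivariate analysis is done there. A major deviation is not defined, and a negative baseline culture is not named as one.

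**Success.** Section 7.1 calls the drug effective in a patient with clinical remission, microbiological remission, or both. For culture, its table gives the value "Must be recorded as absent in 95% of the subjects evaluated". The main criterion in the same section asks instead for a reduction in the number or species of bacteria from baseline.

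**Hypothesis.** Section 6.1 seeks non-inferiority to moxifloxacin and gatifloxacin. No margin is stated.

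**Background.** Section 4.1 puts viral cases at 80% of reported conjunctivitis and adds that "it is estimated that 50% of these will be misdiagnosed as bacterial", judged against culture. The justification section says these infections generally resolve on their own.

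**The concern.** The stated objective is efficacy in bacterial conjunctivitis. An eye with no bacteria at baseline has nothing for an antibiotic to remove, and its recovery says little about which antibiotic was given. If such eyes recover equally often in all five arms, they pull the success rates together. In a superiority trial that would work against the sponsor. Here it works towards the conclusion sought, and it also blurs the comparison among the three PRO-157 posologies.

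The sizing and the analysis do not match either. The specific efficacy behind the smaller sample size in section 23 is the disappearance of a bacterium found before treatment. It is defined only for culture-positive eyes, yet the analysis sets do not ask for one.

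**Working it through.** **1. The plan's own figures.** Annex 1 uses "α = Nivel de significancia o probabilidad de error tipo 1 0.050", two-sided (z = 1.960), and 80% power (z = 0.842). Its continuity correction is m = 0.25·m′·[1 + √(1 + 4/(m′·|P2 − P1|))]².
- Absolute efficacy, 69.8% vs 53.3%: m′ = 135.272 gives m = 147.1 (stated: 147).
- Specific efficacy, 92.34% vs 66.12%: m′ = 36.373 gives m = 43.7, so 44 (stated: 44).

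Both reproduce. The 60 eyes per arm follow from neither, and neither allows for culture-negative eyes.

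**2. Dilution.** Let f be the culture-negative share and q the success rate in those eyes, the same in every arm. The observed rate in an arm is (1 − f)·p + f·q. The f·q terms cancel in a difference, leaving (1 − f) × the true difference. The documents do not give f, so it is assumed below. The 15-point true deficit is also an assumption.

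| f | Culture-positive eyes of 60 | 15-point deficit appears as |
|---|---|---|
| 20% | 60 × 0.8 = 48 | 12 points |
| 30% | 60 × 0.7 = 42 | 10.5 points |
| 40% | 60 × 0.6 = 36 | 9 points |
| 50% | 60 × 0.5 = 30 | 7.5 points |

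**3. Effect on a non-inferiority conclusion.** Assume a 15-point margin, one-sided 0.025, 60 eyes per arm treated as independent, and a true deficit in culture-positive eyes equal to the margin. Then P(declare) = Φ[(0.15 − observed difference)/SE − 1.96], with SE the unpooled standard error.

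Example: f = 40%, control 69.8%, q = 100%.
- Control: 0.6 × 0.698 + 0.4 = 0.8188. PRO-157: 0.6 × 0.548 + 0.4 = 0.7288.
- SE = √[(0.8188 × 0.1812 + 0.7288 × 0.2712)/60] = 0.0759.
- P = Φ(0.06/0.0759 − 1.96) = 12.1%.

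| Control rate, q | f = 0 | 20% | 40% | 50% |
|---|---|---|---|---|
| 69.8%, q = 100% | 2.5% | 5.5% | 12.1% | 18.3% |
| 69.8%, q = 80% | 2.5% | 5.4% | 10.7% | 14.7% |
| 92.34%, q = 100% | 2.5% | 7.4% | 21.1% | 34.8% |
| 92.34%, q = 80% | 2.5% | 6.6% | 14.0% | 19.1% |

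At f = 40% the range over the same four settings is 7.0% to 13.0% for a 10-point margin and 15.5% to 30.6% for a 20-point margin.

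**4. What section 4.1 implies about f.** Of 100 cases, 80 are viral and 80 × 0.5 = 40 of these are labelled bacterial. If the other 20 are all bacterial and all labelled so, the viral share of the labelled group is 40/60 = 67%. If only 15 carry the label, it is 40/55 = 73%.

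**The case against.** The plan has safeguards. Section 15.2 excludes suspected viral or allergic conjunctivitis, and its elimination criteria list both a diagnosis other than acute bacterial conjunctivitis and failure to improve. These reduce the problem without removing it. The exclusion cannot catch viral cases taken for bacterial, and the schedule contains no viral test. The elimination points are left to judgement, and their effect on PP is not stated.

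Several stronger readings are tempting, but the documents do not support them.

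- *Culture-negative patients are written into both efficacy comparisons.* ITT is descriptive; only PP carries the comparison. Their place in PP follows from silence, since major deviation is undefined.
- *A baseline-negative eye is a microbiological success by rule.* That fits the absent value in section 7.1, which is worded as a group threshold. It does not fit the reduction wording in the same section, because an eye without growth cannot be reduced. The clinical route to success does not depend on this.
- *Analysis membership depends on improvement.* Section 15.1 concerns continuing treatment. Stopping removes nobody from ITT, and removes someone from PP only if stopping counts as a major deviation.
- *67% is a ceiling or a forecast.* It is neither. Fewer labelled bacterial cases raise it, and it describes conjunctivitis in general, not patients screened under section 15.2.
- *Culture-negative means viral.* Section 15.2 admits patients given another antibiotic before the baseline day, so some negatives may be bacterial. The justification section says some causative species normally live on the conjunctiva, so a viral eye may grow bacteria.

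**Conclusion.** The point stands. Followed as written, the plan brings patients in and doses them without regard to culture, has no culture-positive set, and accepts clinical remission alone as success. Any true difference between antibiotics is then multiplied by (1 − f), which favours non-inferiority. With an assumed 15-point margin, 69.8% control success and every culture-negative eye succeeding, the chance of wrongly declaring non-inferiority at the margin rises from 2.5% to 5.5%, 12.1% and 18.3% at f of 20%, 40% and 50%.

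These sizes rest on assumed values of f, q and the margin, on equal drug-independent success across arms, and on independent eyes. The direction needs only the equal-success assumption and f above zero. If some culture-negative eyes do respond to the drug, the shrinkage is smaller.

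**What to change.** 1. In section 23, define a baseline-culture-positive efficacy set: all randomised, dosed patients with bacteria isolated at baseline in a study eye, by a pathogen or colony-count criterion fixed in advance, regardless of later improvement, elimination or withdrawal. Use it for the efficacy comparison of PRO-157 with each comparator. The sample is taken before dosing, so this subset keeps the randomised comparison.
2. In section 7.1, score microbiological remission only in eyes positive at baseline, and reconcile the absent and reduction wordings.
3. Keep all dosed patients for safety and as a supportive clinical analysis.
4. State that membership of the efficacy set does not depend on whether treatment continues. The treatment-continuation rule in section 15.1 is a clinical matter and needs no change for this purpose, but it and the elimination criteria in section 15.2 must be reconciled.
5. Restate the expected number of evaluable eyes per arm. At f = 20% the 48 eyes fall below the suggested minimum of 50; at 30% the 42 also fall below the calculated 44.

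**Cost.** No new procedure is needed, since the baseline culture is already taken. The main comparison has fewer eyes and wider intervals. Keeping 60 culture-positive eyes per arm would mean enrolling 60/(1 − f): 75 at 20%, 86 at 30% (60/0.7 = 85.7), 100 at 40% or 120 at 50%.
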